### **8.3.1.2 22-Item Sino-Nasal Outcome Test (SNOT-22) Questionnaire**

The ePRO will also be used to collect responses to the SNOT-22 questionnaire at the time points specified in the Schedule of Events (Section 8.1).

The SNOT-22 questionnaire is a 22-item disease-specific quality of life instrument validated for use in CS  (Section 14.2). Subjects score the severity of their symptoms and social/emotional consequences of CS on a 6-point scale:

- 0 = no problem
- 1 = very mild problem
- 2 = mild or slight problem
- 3 = moderate problem
- 4 = severe problem
- 5 = problem as bad as it can be

The scores are summed; higher scores on the SNOT-22 instrument total score or subdomain scores as defined in Table 2  indicate higher severity of symptoms or social/emotional consequences of CS.

**Table 2: Categorized Survey Items for Separate Domains of the SNOT-22 Instrument**

SNOT-22 Domains	Survey Items	Score Range
Rhinologic Symptoms	#1, #2, #3, #4, #7, #12	0–30
Extra-Nasal Rhinologic Symptoms	#5, #6, #7	0–15
Ear/Facial Symptoms	#3, #8, #9, #10, #11	0–25
Psychological Dysfunction	#16, #17, #18, #19, #20, #21, #22	0–35
Sleep Dysfunction	#13, #14, #15, #16, #17	0–25

SNOT-22 = 22-item Sino-nasal Outcome Test

### 8.3.1.3 Saline Irrigation Use

The ePRO will also be used to collect the frequency of daily saline irrigation by the subjects.

### 8.3.1.4 36-item Short Form Health Survey version 2 (SF-36v2®) Questionnaire

At Day-1, Week 24/EOT, and Week 48/EOS visits, subjects will complete the SF-36v2® questionnaire by ePRO. SF-36v2® is a generic health survey that asks 36 questions to measure functional health and well-being of a subject (Section 14.4). It is a valid measure of physical and mental health and the most frequently used PRO instrument in clinical trials today [30]. Additionally, the SF-36v2® provides scores for each of the eight health domains and psychometrically based physical component summary (PCS) and mental component summary (MCS) scores (Table 3) [31]. The items of the SF-36v2 are transformed and summed to a norm-based scores (Mean = 50, SD = 10) scale for each PCS and MCS domain in which higher scores indicate a better health-related QoL.

**Table 3. SF-36v2® Health Survey Measurement Model**

SF-36v2 Components and Domains	Survey Items
Physical Component Summary (PCS)	
Physical Functioning (PF)	#3a, #3b, #3c, #3d, #3e, #3f, #3g, #3h, #3i, #3j
Role -Physical (RP)	#4a, #4b, #4c, #4d
Bodily Pain (BP)	#7, #8
General Health (GH)	#1, #11a, #11b, #11c, #11d
Mental Component Summary (MCS)	
Vitality (VT)	#9a, #9e, #9g, #9i
Social Functioning (SF)	#6, #10
Role-Emotional (RE)	#5a, #5b, #5c
Mental Health (MH)	#9b, #9c, #9d, #9f, #9h

### **8.3.1.5 End-of-Treatment Questionnaire**

At Week 24/EOT visit, subjects will complete an end-of-treatment questionnaire by ePRO (Section 14.3). The questionnaire will query subjects about their general experience and satisfaction with their assigned study treatment. Subjects will describe their experiences by answering multi-choice questions or providing narrative responses.

### **8.3.2 Sinus Inflammation Imaging**

Sinus inflammation will be assessed by MRI without contrast at the time points specified in the Schedule of Events (Section 8.1), unless medically contraindicated. The Screening MRI should be performed anytime between the Screening and Day 1 visits. The follow up MRI will be conducted within 7 days after the LYR-210 removal/sham procedure at Week 24/EOT visit. If a subject is experiencing or recovering from a cold, acute exacerbation of nasal allergy, or upper respiratory tract infection at the EOT visit, the MRI will be performed 4 weeks after resolution of the adverse event. If a subject requires oral corticosteroid as rescue during the 24-week treatment period, the follow-up MRI should be performed before receiving the rescue treatment instead of at Week 24/EOT visit.

The sinus inflammation will be assessed using the Zinreich modified Lund-Mackay scoring system (referred herein as the Zinreich scores) where each sinus is assigned a score based on the percentage of opacification as follows:

- 0 = 0%
- 1 = 1% to 25%
- 2 = 26% to 50%
- 3 = 51% to 75%
- 4 = 76 % to 99%
- 5 = 100% or completely occluded

The ostiomeatal complex (OMC) is given a score of 0 to 2 as follows:

- 0 = completely patent
- 1 = partially occluded
- 2 = completely occluded

Each sinus pair has a bilateral Zinreich score in the range of 0 to 10, and the OMC pair in the range of 0 to 4, and the total sum of all sinuses and OMCs in the range of 0-54.

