#### **4.1.2 Treatment Stage**

The total duration of the Treatment Stage will be 24 weeks. Subjects who complete the study Screening assessments and the washout period and meet all eligibility criteria on Day 1 will be stratified according to the presence or absence of nasal allergy and nasal polyps and, then, randomized in a 1:1:1 ratio to receive LYR-210 (2500 µg), LYR-210 (7500 µg), or sham procedure. Subjects who are assigned to the experimental arms will have the LYR-210 administered bilaterally into the middle meatus (Section 6.2) and, then, removed at Week 24 (Section 6.5). Subjects who are assigned to the sham procedure arm, will undergo bilateral mock administration (i.e., sham procedure) on Day 1. Enrolled subjects will undergo scheduled study visits at Weeks 2, 4, 12, and 24 during the treatment duration. Subjects will receive phone follow-ups at Weeks 8, 16, and 20 to record AEs and concomitant medications/procedures that they have had since last follow-up assessment. [NOTE: Female subjects of childbearing potential will be asked to return to the clinic for urine pregnancy test at Weeks 8, 16, and 20.] All subjects will remain blinded and undergo the assessments and procedures scheduled for these visits (Section 8.1).

At the Week 24 visit, all subjects will return to clinic for the **end-of-treatment (EOT)** visit assessments. Subjects who receive LYR-210 will have bilateral depot removed using standard surgical tools. Sham control subjects will undergo a sham removal procedure to remain blinded.

If medically warranted per the treating physician's discretion (for example, needing an ESS as rescue treatment), early depot removal before the schedule EOT visit at Week 24 may be performed at an unscheduled **early-termination (ET)** visit (an unscheduled EOT visit). Any subject who undergoes an ET visit is required to complete the assessments scheduled for the Week 24/EOT visit, and all safety follow up visits post treatment.

If spontaneous dislodgement of LYR-210 occurs before Week 24 in subjects who receive either dose of LYR-210, subjects are required to call the study clinic immediately to report the event. If

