### **4.3 Discontinuation of Study Subjects**

Subjects will be encouraged to complete the study through the treatment and post-treatment follow up periods. Each subject is free to discontinue from the study at any time, for any reason, and without penalty or loss of benefit. Participation in the study treatment may be discontinued for any of the following reasons:

- Occurrence of any medical condition or circumstance that exposes the subject to substantial risk and/or does not allow the subject to adhere to the requirements of the protocol, including early removal of LYR-210 (Section 6.5).
- Any serious AE (SAE, Section 8.4.9.2), clinically significant AE, severe laboratory abnormality, intercurrent illness, or other medical condition that indicates to the Investigator that continued participation is not in the best interest of the subject.
- Subject's decision to withdraw.
- Requiring ESS as rescue treatment.
- If deviations to the use of prohibited medications occur after randomization and study treatment, the Investigator in consultation with the Sponsor and Sponsor's medical monitor will decide on a case-by-case basis whether the subject may continue in the study based on the time the prohibited medication was administered and its pharmacology.
- Subject's failure to comply with protocol requirements or study related procedures.
- Termination of the study by the Sponsor or a regulatory authority that has provided approval to proceed.

Subjects who withdraw or are withdrawn from the study treatment will be requested to return to the clinic for the assessments and procedures scheduled for the EOT visit and the safety follow up visits post EOT (Section 8.1).

The Investigator or study staff will document the reason(s) for subject discontinuation on the Case Report form (CRF), notify the IRB/EC as required by their Institution's procedures, and notify the Sponsor the reason for discontinuation.

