#### **6.4.4 Rescue Concomitant Medications and Treatment**

The following rescue medications are recommended in the event of an acute exacerbation of the following conditions that result in the subject contacting the Investigator who determines an initiation of rescue therapy:

- Any time during the 24-week treatment stage:
  - After a clinic visit and per Investigator's judgment, antibiotics for sinus infection.
  - After a clinical visit and evaluation for worsening or uncontrolled severe CS symptoms, the Investigator using his/her best judgement may give a course of oral corticosteroids. Typical indications include persistent sinus infection after an initial course of antibiotics while starting another course of antibiotics, uncontrolled sinus inflammation not responding to an INCS, or a flare-up of asthma. The rationale for the use of oral corticosteroid must be recorded.
- After the Week 4 visit only:
  - For acute allergic symptoms: non-sedating oral antihistamine such as loratadine (10 mg per day) or equivalent.
  - For severe acute nasal blockage (score of 2 or more over the past 3 days): a course of oxymetazoline spray for a maximum of 3 consecutive days and a total maximum of 10 days during the treatment period. Oxymetazoline cannot be used within 24 hours before MRI assessments.
  - For worsening CS symptoms: intranasal MF sprays with dose and duration per Investigator's recommendation.
  - For worsening or uncontrolled severe CS symptoms: ESS as rescue treatment per Investigator's recommendation.

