#### **6.5 Removal Procedure**

Subjects who receive LYR-210 will have the bilateral drug depots removed at the Week 24/EOT visit or earlier in an Unscheduled early termination (ET) visit if medically warranted per the treating physician's discretion (for example, requiring an ESS as rescue treatment). The removal procedure will be performed under endoscopic visualization after topical anesthetic and decongestant sprays applied to each nostril. Standard surgical tools are used to remove LYR-210. LYR-210 is made of polymers designed to gradually soften over time. Care should be taken to remove LYR-210 in one piece or in sections should any disintegration of LYR-210 occur.

To keep the subjects enrolled in the sham procedure group fully blinded in the post-treatment safety follow up stage, all sham control subjects will undergo a sham removal procedure either at the scheduled Week 24 visit or earlier in an unscheduled early termination (ET) visit if the subjects request early depot removal.

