15.2.4.2. Analysis of Zinreich Score

The number and percentage of subjects at Week 24 in the ITT analysis set with and without at least a 1-point decrease in one of the six bilateral Zinreich sinuses score as defined in Section 15.2.1.2 will be provided by treatment group.

A logistic regression adjusting for the baseline total bilateral Zinreich score and stratification variables (nasal allergy and nasal polyps) will be used to compare treatment groups. The responder indicator will be set to 1 for subjects who achieve at least a 1-point decrease in any score at Week 24 compared to baseline. Subjects for whom the decrease cannot be calculated, for example due to early termination, will be excluded from the analysis.

Odds ratios together with the 90% CI will be presented to compare treatment groups. This analysis will be repeated for the PP analysis set.

As non-key secondary analyses, the CFBL in each of the 5 bilateral Zinreich sinuses score, Zinreich OMC score and total Zinreich score at Week 24 will be analyzed using an ANCOVA model as specified in Section 15.1.3 replacing the baseline CS7DA4S with the appropriate baseline bilateral Zinreich sinuses score, Zinreich OMC score or baseline Zinreich total score. This analysis will be repeated for the PP analysis set.

Additionally, the logistic regression and ANCOVA models will be repeated on the subgroups as per baseline median total bilateral Zinreich score, for the ITT analysis set.

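### The protocol places the follow-up MRI before oral corticosteroid rescue but not before ESS rescue, and no scoring rule makes a subject who had ESS a non-responder on the key secondary Zinreich endpoint

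*Protocol*

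**What the plan says.** **MRI timing.** Protocol 8.3.2 sets the default: "The follow up MRI will be conducted within 7 days after the LYR-210 removal/sham procedure at Week 24/EOT visit". For steroid rescue it adds: "If a subject requires oral corticosteroid as rescue during the 24-week treatment period, the follow-up MRI should be performed before receiving the rescue treatment", and that scan replaces the Week 24/EOT one. The Synopsis, Section 8.1 and the footnotes to Table 1 repeat this. All name oral corticosteroid only.

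**ESS as rescue.** After the Week 4 visit, Protocol 6.4.4 allows: "For worsening or uncontrolled severe CS symptoms: ESS as rescue treatment per Investigator's recommendation".

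**Indirect cover for ESS.** Need for ESS is the protocol's own example for early removal in Section 4.1.2: "for example, needing an ESS as rescue treatment), early depot removal before the schedule EOT visit at Week 24 may be performed". The same section says: "Any subject who undergoes an ET visit is required to complete the assessments scheduled for the Week 24/EOT visit". Section 4.3 lists "Requiring ESS as rescue treatment" among the reasons for which study treatment may be discontinued, after which subjects are asked back for the EOT assessments. For sham subjects, Section 6.5 provides removal at Week 24 or "earlier in an unscheduled early termination (ET) visit if the subjects request early depot removal".

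**Analysis.** SAP 15.2.4.2: "The responder indicator will be set to 1 for subjects who achieve at least a 1-point decrease in any score at Week 24". Subjects whose decrease cannot be calculated, with early termination as the example given, are left out. SAP 6.6 assigns early-termination and unscheduled assessments to visits by study day; Week 24 is Day 156 to 183. SAP 6.5 keeps the pooled EOT timepoint out of all models. Protocol 10.6.2.2 instead takes ITT subjects with any available post-treatment MRI.

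**The concern.** The protocol recognises that rescue can contaminate the MRI endpoint and deals with oral corticosteroids. ESS operates on the sinuses being scored, yet neither the scan timing nor the responder definition mentions it. A subject whose assigned treatment ended in surgery can therefore be counted as an MRI success, or disappear from the analysis, depending on when the scan was taken.

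This also sets two key secondary endpoints against each other. Under Protocol 10.6.2.3 and SAP 15.2.1.3, an ESS recommendation for worsening CS symptoms is a treatment failure. The same subject can be a responder on the Zinreich endpoint. The per-protocol set does not resolve this: SAP 5.6 asks for at least 16 weeks of exposure but does not list ESS as a reason for exclusion.

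**Working it through.** **1. The plan's own figure.** The MRI endpoint has no power statement. The only powered comparison is the primary one: difference 3.00 − 1.30 = 1.70, SD 2.4, 21 per arm, one-sided 0.05. The standardised difference is 1.70 / (2.4 × √(2/21)) = 2.295. Normal approximation: Φ(2.295 − 1.645) = 74.2%; noncentral t with 40 df: 73.0%. The stated 73% reproduces for one dose against sham. Only the 21 per arm and the one-sided 0.05 are carried forward.

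**2. Tracing a subject who has ESS through the rules.**

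- *ET visit on Day 141 (Week 20).* The MRI is due within 7 days of removal, so by Day 148. SAP Table 1 maps Day 148 to Week 20 (Day 128 to 155). There is no Week 24 value and the subject is excluded.
- *Scan on Day 156 to 183 after ESS.* This can arise if there was no ET scan and the subject attended Week 24, if the subject was scanned again at Week 24, or if the ET visit was late. The scan is a Week 24 value, and a 1-point decrease makes the subject a responder. (For a rescan after an ET visit, the SAP does not say whether the Week 24 window or the post-treatment window applies.)
- *Protocol 10.6.2.2.* Any available post-treatment MRI counts, including one taken after ESS at an ET visit.

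No route yields non-response because of the surgery.

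**3. The same windowing applied to the steroid rule.** A pre-steroid scan on Day 100, say, falls in the Week 16 window (Day 100 to 127). The protocol means it to stand in for the Week 24 scan, but under the SAP it is not a Week 24 value.

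**4. Effect within one arm.** One subject is 1/21 = 4.8 points. Suppose 10 of 21 respond, with the ESS subject a non-responder: 10/21 = 47.6%. Excluding that subject gives 10/20 = 50.0%; scoring the subject as a responder gives 11/21 = 52.4%. Both raise the rate of the arm in which the ESS occurred.

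**5. Illustrative power.** With p1 the sham rate, p2 the LYR-210 rate, d = p2 − p1 and p̄ their mean, power = Φ[(d − 1.645 × √(p̄(1 − p̄) × 2/21)) / √((p1(1 − p1) + p2(1 − p2))/21)]. For 50% against 80%: (0.300 − 1.645 × 0.1472) / 0.1397 = 0.414, giving 66.1%. With one sham non-responder turned into a responder, p1 = 0.548: (0.252 − 1.645 × 0.1447) / 0.1393 = 0.103, giving 54.1%.

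| Assumed sham vs LYR-210 | None | 1 | 2 | 3 misclassified in sham |
|---|---|---|---|---|
| 40% vs 80% | 86.4% | 77.8% | 67.2% | 55.3% |
| 50% vs 80% | 66.1% | 54.1% | 41.9% | 30.3% |
| 60% vs 85% | 57.0% | 44.6% | 32.4% | 21.5% |

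The loss per subject lies between 8.6 and 12.4 points. All rates are assumptions, as are full conversion by ESS and all cases being in sham.

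**The case against.** The strongest reply is that the protocol does reach ESS. Need for surgery is its own example for early removal, an ET visit carries the EOT assessments including the MRI, and requiring ESS is a reason to stop treatment in every arm. A reader might infer that ESS is not covered at all; the documents do not support that. What stands is that the cover is loose. Early removal and discontinuation are optional, return for EOT assessments after withdrawal is requested, and the early sham removal in Section 6.5 depends on the subject asking. The scan is timed from removal, not from surgery.

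A reader might also infer that every post-ESS scan is scored as response. Under the SAP it is not: only scans on Day 156 to 183 count, and earlier ET scans lead to exclusion.

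A third tempting inference is that the gap hides an LYR-210 effect because sham subjects more easily reach Week 24 after ESS. The documents give no ESS rate by arm. Dropping LYR-210 subjects who left early for ESS would flatter LYR-210, and Section 4.3 applies to both arms. The net sign cannot be stated.

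It is also fair to say that the study is declared exploratory with nominal p-values (SAP 7.8), that an ESS recommendation already counts in time to treatment failure, and that non-response is one estimand among several. These points lower the stakes, but the handling of ESS still needs to be stated.

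**Conclusion.** The concern holds in a limited form. No section orders the follow-up MRI against ESS, and no analysis rule makes a subject who had surgery a non-responder. A post-ESS scan in the Week 24 window can count as response, and an ET scan before Day 156 removes the subject. The same windowing defeats the protocol's substitution of the pre-steroid MRI when that scan precedes Day 156.

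The size is 4.8 points of response rate per misclassified subject at 21 per arm. The accompanying 8 to 13 points of power per subject is an illustration: it assumes the response rates shown, cases only in sham, and a post-ESS scan that improves by at least 1 point. It is not an estimate of what will happen. The inconsistency between two key secondary endpoints and the low cost of a rule are sufficient reason to change the SAP.

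**What to change.** In SAP 15.2.1.2 and 15.2.4.2:

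- Score a subject who had ESS before the follow-up MRI as a non-responder in the key secondary analysis, whether or not a Week 24 scan exists.
- Do not use post-ESS scans for change from baseline in Zinreich scores.
- Add a sensitivity analysis using scans as observed.
- State that a pre-rescue MRI which the protocol substitutes for the Week 24 scan is the Week 24 value, regardless of the Table 1 windows.

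First confirm that ESS dates can be retrieved from the concomitant procedures record. SAP 3.3 says data for the endpoint on need for medical or surgical treatment were not collected. If dates are not available, use the ESS recommendation on the Follow-up eCRF and say that it is a recommendation, not an operation.

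Reconcile Protocol 4.3, 6.4.4, 6.5, 8.3.2 and 10.6.2.2 with SAP 6.5, 6.6 and 15.2.4.2. How rescue, removal and scanning are managed clinically is for the sponsor to settle; no clinical rule is proposed here.

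The cost is a small amount of programming and no extra scan. The endpoint becomes a composite of MRI response and absence of surgery, and should be described as such.

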### **8.3.3 Nasal Polyp Assessment**

Visualization and assessment of nasal polyps will be conducted using endoscopy at the time points specified in the Schedule of Events (Section 8.1). At the Day 1 visit, prior to the LYR-210 administration/sham procedure, an endoscopic assessment of nasal passageway for eligibility will be conducted after topical anesthetic and decongestant sprays are administered, but before any

anesthetic and decongestant soaked pledget or cottonoid is applied for the LYR-210 administration/sham procedure. The follow up endoscopic assessment of the nasal passageway will be conducted at Weeks 2, 4 and 12, Week 24/EOT, and Week 28 visits.

Investigators will evaluate the severity of nasal polyps in the middle meatus at the Week 24/EOT and Week 28 visits by grading polyp severity as “better,” “worse,” or “the same” in comparison to the Baseline severity evaluated at Day 1 visit before the insertion procedure.

#### **8.3.4 The University of Pennsylvania Smell Identification Test (UPSIT™)**

The UPSIT will be conducted at 3 time points during the study as specified in the Schedule of Events (Section 8.1). At Day 1 and Week 24/EOT visits, the UPSIT™ will be conducted prior to the LYR-210 administration/sham procedure and prior to the LYR-210 removal/sham procedure endoscopy assessment.

The UPSIT™ is composed of 40 odorants embedded on scent strips that are released when scratched with a sharply tipped object. The UPSIT is comprised of 4 booklets, each containing 10 microencapsulated (scratch & sniff) odors. The UPSIT is a forced-choice test, and subjects will be instructed to identify each odorant with alternatives accompany each test item. The total olfaction score using the UPSIT is defined as the number of odorants correctly identified out of the 40 odors tested, with higher scores designating better olfactory performance.

### **8.4 Assessment of Safety**

#### **8.4.1 Physical Examination**

A physical examination including a careful assessment of all body systems, including the skin, eyes, ears, nose and throat, respiratory will be performed at all clinic visits as specified in the Schedule of Events (Section 8.1). Height (cm) will only be measured at Screening visit. Weight (kg) and body mass index (BMI) will be measured at all visits.

